6.0 FOOD ANALYSIS PROCEDURES

DELTA Protocol I

Food Collection and Shipping

The FALCC will supply each field center with the materials and SOP for collection and shipping menus and unit foods. Food collection containers will be pre-labeled and pre-weighed. The food collection and shipping procedure should be followed exactly at each field center. Each field center will be requested to report any deviations to the FALCC, which will document such occurrences. All shipments of food will be made with either dry ice or frozen (-20°C) cold packs via overnight delivery.

Log-in

Each container of food will be weighed, and the weight will be logged into the FALCC sample database. All samples will be stored at -20°C or lower until composited.

Compositing

Each food sample (menus and unit foods) will be composited according to the appropriate Standard Operating Procedure for that sample:

Diet validation. For diet validation, each menu and each unit food for each diet (prepared in duplicate) will be individually composited.

Monitoring. Each diet cycle throughout the feeding study, a diet cycle composite will be prepared for each diet.

Sample distribution

All composited samples will be stored at -60°C or lower:

Archive samples

Archive samples will be stored for the duration of the DELTA study. Place five (5) samples (see Appendix C) of each composite into the archive location designated by supervisor. The dispensation of these samples requires approval by the Steering Committee.

Assay samples

Assay samples will be used for the nutrient assays specified below. Any samples that remain after completion of the nutrient assays will be retained for a minimum of 3 months from the completion of Protocol I.

Reserve samples

Reserve samples are extra samples taken by FALCC to accommodate repeat assays, additional assays, etc. There will be a minimum of eight (8) reserve samples per composite. Reserve samples will be used at the discretion of the FALCC. Any samples that remain after completion of the nutrient assays will be retained for a minimum of 3 months from the completion of Protocol I.

Assay Quality Control

Control samples: For each assay, a control sample (mixed diet composite) will be included with each batch of samples or at least every 20 samples, whichever is less.

QC charts: A QC chart will be established for each assay. Prior to running samples, a minimum of 15 samples of the control material will be assayed, according to the assay SOP. The mean and $\pm 2*SD$ and $\pm 3*SD$ will be calculated from these data and plotted as a QC chart. The value for the control material in each assay batch will then be plotted on the QC chart. If the control value falls outside the $\pm 3*SD$ limits, the assay will be rejected. The procedure will be evaluated for possible sources of error, corrected if indicated, then samples will be rerun.

Blinded samples: An internal sample numbering system will be used so that the analyst cannot decipher information about a sample from its number. In this way, analyst bias will be minimized. The sample database maintains a link between the sample number and all information concerning that sample. The identity of samples will not be disclosed to the analysts prior to performing assays.

SOPs: FALCC will write Standard Operating Procedures (SOPs) for all nutrient assays and laboratory procedures. Each SOP will be signed and dated. Original copies will be kept in a central notebook with disk copies on file as well. Non-current SOPs will be archived.

Assays methods and validation

Total fat

Method: Total lipid will be determined gravimetrically after extraction of the diet composites with chloroform/methanol (modified AOAC 983.23, 1990; see Appendix G4).

Validation: Validation of the method will be based on acceptable recovery of canola oil spiked into composited mixed diets, and acceptable results for standard reference material (NIST SRM #1548¹). Results will also be compared to data obtained by NCL using acid hydrolysis and modified Folch assays.

¹National Institute of Standards and Technology (NIST), Gaithersburg, MD

Cholesterol

Method: The method of [name] [Thompson and Merola [USDA Nutrient Composition Laboratory (NCL), Beltsville, MD, 1992], with modifications, will be used to quantify cholesterol (see Appendix G5). The method has been adapted as follows: 1) GC analysis with temperature programming (60°C hold 1 min., then 30°C/min. to 270°C hold for 20 min.) instead of isothermal at 267°C, 2) GC split ratio decreased to 1:20, 3) injection volume decreased to 0.5 μ l, 4) cyclohexane added before water in saponification step of sample preparation, 5) 250 μ l of derivatization reagent used.

Validation: Validation of the method will be based on acceptable recovery of cholesterol spiked into mixed diet composites, acceptable results for standard reference material (fortified coconut oil, NIST #1563-2), agreement of results with those obtained by [name] for EZ menus analyzed for Pilot Study #1, and favorable comparison with independent measurements of the cholesterol content of the control sample by NCL.

Moisture

Method: Moisture in the diet composites will be determined with a microwave moisture/solids analyzer (CEM Corp.) (Appendix G6). Moisture will be measured in triplicate for each diet composite. These results will be used to calculate all assay results for the composite on a dry weight basis.

Validation: Validation of the method will be based upon favorable comparison of results by microwave drying (FALCC SOP #5007, App. G6) with those from conventional vacuum oven drying (AOAC 934.01, modified; Appendix G7), acceptable results obtained for NCL reference sample #Q93-FR-4495 used in Pilot Study #1 assays of EZ menus, and favorable comparison of FALCC moisture data for the control sample with those obtained independently by NCL.

Fatty acids (saturated, monounsaturated, polyunsaturated, omega-3)

Method: Fatty acid composition will be determined by gas-liquid chromatography of fatty acid methyl esters prepared from the saponified lipid extracts of diet composites (chloroform/methanol extracts, as prepared for total fat, Appendix G4) (AOCS Official Method Ce 1b-89; 1991, modified). The AOCS method has been adapted to separate and quantitate C:10 and higher fatty acid methyl esters (FAMES) by lowering the initial temperature (from 170°C to 150°C) (see Appendix G8). The injection volume was also decreased. FAMES will be reported as triacylglycerol equivalents (TAGs) according to the classification scheme shown in. Fatty acids as TAGs will be normalized to the total fat content (determined as described above).

Validation: Validation will be based upon acceptable fatty acid recoveries from canola oil spiked into diet composites, and favorable comparison of FALCC data for the control sample with those obtained independently by NCL.

Ash

Method: Ashing will be accomplished by vacuum-drying wet diet composite samples, then heating until at 550C in a muffle furnace until completely ashed (Appendix G10).

Validation: Validation will be based upon acceptable ash content determined for NIST SRM #1548, and favorable comparison of FALCC ash data for the control sample with those obtained independently by NCL.

Protein

Method: Protein will be determined as Kjeldahl nitrogen x 6.25. FALCC will subcontract Kjeldahl assay to the Dept. of Human Nutrition and Foods (HNF) at Virginia Tech, which has a semi-automated system. FALCC control samples (blinded) and HNF internal QC samples will be included in each assay batch.

Validation: Validation of the method will be based on acceptable results obtained for NIST SRM #1548, and favorable comparison of results for the control sample with data obtained independently by NCL.

Dietary Fiber

Method: AOAC method 991.43 will be used to measure total dietary fiber. The procedure will be modified for the assay of wet homogenized diet samples instead of ground freeze-dried samples (see Appendix K).

Validation: Validation of the method is based on acceptable results for NIST SRM #1548, and AOAC dietary fiber collaborative study samples². Any modifications to the AOAC method will be validated in this way as well.

²Lee et al., JAOAC Intl., 75: 395-416, 1992.

Data to be reported

component	units
total fat	g/100g dry weight
total SFA	g/100g dry weight (as triglycerides)
total MUFA	g/100g dry weight (as triglycerides)
total PUFA	g/100g dry weight (as triglycerides)
EPA ³	g/100g dry weight (as triglycerides)
DHA ³	g/100g dry weight (as triglycerides)
α-L ³	g/100g dry weight (as triglycerides)
cholesterol	mg/100g dry weight
protein	g/100g dry weight
ash	g/100g dry weight
dietary fiber	g/100g dry weight
moisture	g/100g
total weight	grams

Calculated:

total dry weight ⁴	grams
carbohydrate ⁵	g/100g dry weight
total energy ⁶	kcal
total fat ⁷	% of total kcal
SFA ⁸	% of total kcal
MUFA ⁹	% of total kcal
PUFA ¹⁰	% of total kcal

³EPA: eicosapentaenoic acid; DHA: docosahexaenoic acid; α-L: α-linolenic acid

⁴total wet weight * (1-%H₂O/100)

⁵100 - g protein/100g dry wt - g ash/100g dry wt - g total fat/100g dry wt

⁶total kcal = [g protein/100g dry wt + g CHO/100g dry wt)*4 + (g total fat/100g dry wt)*9] * total dry wt/100

⁷(g total fat/100 g dry wt)*9*total dry wt/100
 _____ *100
 total kcal

⁸(g SFA/100 g dry wt)*9*total dry wt/100
 _____ *100
 total kcal

⁹(g MUFA/100 g dry wt)*9*total dry wt/100
 _____ *100
 total kcal

¹⁰(g PUFA/100 g dry wt)*9*total dry wt/100
 _____ *100
 total kcal

Calculated:

component	units
EPA ¹¹	% of total kcal
DHA ¹¹	% of total kcal
α-L ¹¹	% of total kcal

Laboratory Quality Assurance

Instrument/equipment calibration

All balances, instruments, and equipment will be calibrated at least weekly, and more frequently if appropriate. The temperature of refrigerators and freezers is monitored daily. Balances will be calibrated using the protocol and standard weights specified in the DIET MOP.

Audit trail

Because of the large volume of samples and the complexity of processing and assaying samples, the FALCC has developed an internal database to assign numbers and keep track of data concerning any given sample. The database will maintain a link between any given whole food sample and its composited subsamples and all related data and assay results.

Storage of data

Electronic data will be stored on hard drives and floppy disk. Computers will be backed up weekly. Disk copies and hard copies of all data will be archived.

$$\frac{^{11}(\text{g FA}/100 \text{ g dry wt}) \cdot 9 \cdot \text{total dry wt}/100}{\text{total kcal}} \cdot 100$$

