The snack will always be a packed meal. Follow procedure for other packed meals. Check back items using the participant's self report from the **SNACK FORM** list when the participant returns the following day.

UNIT FOODS

Check the appropriate box and enter the number of units for each unit food provided. Check back using participant's self report from the **PACKED MEAL** form. Record the total number of Unit Foods consumed in item #11 on the front of the DDFR. Participants are expected, but not required, to consume all of the unit foods provided once they are stabilized on a calorie level.

NON STUDY-PROVIDED FOODS

This section is filled in from self reported information on the **PACKED MEAL and SNACK** forms which will be obtained on the following day when the participant returns for breakfast. Items eaten at the self-selected meal (if used by participant) should be listed on the Packed Meal Form by the participant and then transferred to the back of Saturday's DDFR by study personnel.

[figure not shown]
CODING

When all study-provided foods have been checked back, count the number of boxes checked as not completely eaten and enter this number in the box for item 5. If no boxes were checked, enter "0". Count the number of boxes checked for breakfast, lunch, dinner and snack only. **Do not include the number of unit foods in this total.**

For coding non-study provided foods, evaluate each food item recorded and enter "0" in the code box if the item was non-caloric, and "1" for caloric items. Sum the numbers in the **Total** box and enter this number in item 6.

Alcoholic beverages should be listed as number of drinks. Enter the number for each kind of alcoholic beverage reported and sum the numbers in the **Total** box. Enter this number in item 7.

If no additional foods or alcoholic beverages were reported, enter "0" for items 6 and 7.

DAILY FOOD RECORD (DDFR)

Name _____

1. DELTA I.D. _____ 2. Date ____ mm ____ dd ____ yy 3. Day of Week _____ 4. Menu 1, 2000 Kcal Diet A 5. No. of study items not eaten

6. Other items 7. No of alcoholic beverages 8. Was BREAKFAST packed? Yes No 9. Was LUNCH packed? Yes No

10. Was DINNER packed? Yes No 11. No. of Unit Foods eaten

BREAKFAST

Assembled/
Served

- 124.5g Orange juice
- 28.4g Bran flakes
- 50.4g PF, Whole Wheat toast
- 9.0g Butter
- 2 tsp Grape jelly (1 pc)
- 245.0g Whole milk
- Free beverage

Check any item
not completely
eaten*

LUNCH

Assembled/
Served

- Turkey sandwich

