- 50.0g Sliced turkey breast
- 45.4g PF sandwich white bread
- 4.5g Mayonnaise
- 1/4 cup Lettuce
- 21.8g Ginger cookie
- 100.0g Peach slices
- Free beverage

Check any item
not completely
eaten*

COMMENTS: _____

COMMENTS: _____

Food server code _____ Checker code _____

Food server code _____ Checker code _____

**If item was added to another meal, do not check the column, write the item in the meal where it was added.*

DINNER

Assembled/
Served

Check any item
not completely
eaten*

- 1 sv Sirloin tips/gravy/egg noodles
- 100.0g Green peas
- 1 sv Tossed Salad
- Salad Dressing:
 - 1.5g Olive oil
 - 1 TB Fat free French dressing
- 37.8g Country classic roll
- 10.0g Butter on roll
- 108.8g Applesauce
- Free beverage

COMMENTS: _____

Food server code _____ Checker code _____

*If item was added to another meal, do not check the column, write the item in the meal where it was added.

INFORMATION FOR THIS SECTION IS TRANSCRIBED FROM THE PACKED MEAL FORM ON THE FOLLOWING DAY.

Were any foods or beverages eaten that were not provided by the DELTA Center (Except for Free Beverages)?
 Yes No If Yes, please list. List alcoholic beverages separately.

Food Item	Amount	Description	Code	Type	Alcoholic Beverages # of Drinks
					
					
					
TOTAL					

CODING: Count the NO. of items checked as not eaten and enter this NO. in Q5. For non-study foods, code each item as 1.

SNACK

Assembled/
Served

Check any item
not completely
eaten*

- 54.0g Trail mix

UNIT FOODS

of
Units

- Banana muffin
- Carrot muffin
- Roll

COMMENTS: _____

Food server code _____ Checker code _____

5.8.4 Instructions for filling in the DELTA PACKED MEAL Form (PMF) and SNACK Form

The **DELTA PACKED MEAL (PMF)** form (page 5-42) or the **SNACK** form (page 5-43) will be used for all carry out foods. These forms will be used by the participant to verify meals and other foods and beverages consumed off site. They will be used by center staff to transcribe relevant information to the **DELTA DAILY FOOD RECORD** form for coding. The **DELTA PACKED MEAL and SNACK** forms will not be keypunched, and will remain at the local site.

Before filling in the form, first verify that the menu number matches the corresponding menu number on the **DDFR**.

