Highlight *AUTOSYS -_0;B* by clicking on the ↓ key. Click on the ⇒ button next to the Sequence File Name, double click on [*fame*] and highlight the sequence file that was created in steps 4.3 through 4.11. Click on *OK*. Type in the Operator Initials, and click on the *Verify* button. The sequence will then be downloaded to the GC. From the *Data Acquisition* screen, click *Inst*, then *Start*.

- 4.20 Make sure the printer is turned on and paper is loaded into the paper tray.
- 4.21 SHUTDOWN procedure: After the last sample run has been completed, in the *Data Acquisition* Screen of the *Aquire* menu click on *Comm* (for Communication). Click *Release Control*, highlight *AUTOSYS -_0;B* and click *OK*. Then click on the *minus sign* box in the top left-hand corner of the screen and click *Close*. On the GC, turn off the split, air and hydrogen knob valves, and turn off the air and hydrogen tanks (**not the Helium tank!**). On the GC control panel, press the *DET TEMP* button and press *OFF* (black button) then *Enter*. Then press *INJ TEMP*, type in 100 and *Enter*, then press *OVEN TEMP*, punch in 50 and press *ENTER*. The GC is now shut down and the computer and printer can be turned off as soon as all chromatograms are printed.
- 4.22 Remove the caps of the crimp-seal vials using the decapper. Reseal the vials with new caps and mark the level of the liquid in the vial. Store the vials in a freezer.

5. Calculations

- 5.1 The results consist of a chromatogram and a report and will be printed automatically by the computer. The *Adjusted Amounts* are μg of fatty acid methyl esters per sample. In addition, the program generates an ASCII file that will be used for further quantitation (SOP#5025). Punch holes in the reports and place them in the fatty acid data notebooks.

6. Reference(s)

- 6.1 PE Nelson Turbochrom 3 User's Guide 1992
- 6.2 All figures were obtained directly from the Turbochrome 3 software (version 3.3)

Prepared by:

[name]

Approved by:

[name]

Date: _____

Date: _____

CLASSIFICATION OF FATTY ACIDS

SFA	MUFA	PUFA	omega 3-FA	other
10:0	14:1	18:2*	18:3n-3 (α -linolenic)	Other FA
11:0	16:1	20:2	20:5n-3 (EPA)	Unidentified peaks
12:0*	17:1	20:3	22:6n-3 (DHA)	
13:0	18:1*	20:4		
14:0*	19:1	22:6		
15:0	20:1			
16:0*	22:1			
17:0				
18:0*				
20:0				
22:0				
24:0				

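### The diet assay reports total SFA but quantifies only C10 and longer acids, so any C4-C8 saturated acids from butter and whole milk are left out of the documented saturated fat.

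*Protocol*

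**What the plan says.** Four statements in the protocol bear on this.

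- **What the instrument measures.** Section 6.0, under fatty acids: "The AOCS method has been adapted to separate and quantitate C:10 and higher fatty acid methyl esters (FAMES". The table headed "CLASSIFICATION OF FATTY ACIDS" at the end of section 6.1.8 lists the saturated class from 10:0 to 24:0; 4:0, 6:0 and 8:0 do not appear. It also has an other column for other and unidentified peaks.
- **What the result is scaled to.** Section 6.0: "Fatty acids as TAGs will be normalized to the total fat content". Total fat is defined without a chain-length limit: "Total lipid will be determined gravimetrically after extraction of the diet composites with chloroform/methanol". Section 6.1.3 shows that the extract is dried and weighed.
- **What is reported.** The reporting list in section 6.0 names total SFA, MUFA and PUFA per 100 g dry weight and converts each to percent of total kcal. None carries a chain-length qualifier.
- **What is in the food.** The only daily food record shown (section 5.8.3, Diet A, Menu 1, 2000 kcal) has 9.0 g butter and "245.0g Whole milk" at breakfast, and "10.0g Butter on roll" at dinner. Section 5.1 puts whole milk at 3.25-3.3% fat.

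**The concern.** The numerator and denominator of the SFA figure cover different things. Fat weighed by gravimetry includes triglyceride-bound short-chain acids, while the chromatographic classes exclude them. That milk fat contains C4:0-C8:0 saturated acids is general chemistry that the protocol does not mention, and section 6.0 gives no correction for them.

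Saturated fat is one of the two dietary components that define the diets (section 1.0.2, aim 1), and the food laboratory's task is to verify that the diets have the planned content (section 1.1.2.1). An omission that grows with dairy fat is systematic: assaying more composites does not average it out. It could make an on-target diet look low in SFA, and it could shift the documented SFA difference between diets.

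The planned checks may not expose it. Section 6.0 states: "Validation will be based upon acceptable fatty acid recoveries from canola oil spiked into diet composites". The continuing calibration standard in section 6.1.8 is a rapeseed oil mix. Neither is a milk fat.

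**Working it through.** The protocol gives no figure of its own to reproduce, so this is a mass balance for the one menu shown.

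**Inputs from the protocol**
- Butter 9.0 + 10.0 = 19.0 g; whole milk 245 g (section 5.8.3)
- Whole milk fat 3.3% (section 5.1)
- Energy 2000 kcal; 9 kcal per g fat (section 6.0 energy formula)
- Highest fat level 37% of energy (substitution list, section 5.7.7). The list does not name diets by letter, so Diet A = 37% is inferred.

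**Assumptions not in the protocol**
- Butter is 80% fat
- C4-C8 is 4-10% of milk fat
- True SFA, S, is 14-17% of energy

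**Step 1, milk fat.** 19.0 × 0.80 + 245 × 0.033 = 15.2 + 8.1 = 23.3 g. Total fat is 0.37 × 2000 / 9 = 82.2 g, so milk fat is about 28% of it.

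**Step 2, mass not quantified.** 23.3 × 0.04 = 0.93 g; 23.3 × 0.10 = 2.33 g. As a percent of energy, m = grams × 9 / 2000 × 100, giving 0.42 to 1.05.

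**Step 3, SFA if the detected peaks are scaled to total fat.** With T = 37, reported SFA = (S − m) × T / (T − m), so the shortfall is m × (T − S) / (T − m). It is positive whenever m > 0 and S < T.

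| m (% energy) | True S | Shortfall (points of energy) | Relative to S |
|---|---|---|---|
| 0.42 | 14 | 0.42 × 23 / 36.58 = 0.26 | 1.9% |
| 0.42 | 17 | 0.42 × 20 / 36.58 = 0.23 | 1.4% |
| 1.05 | 14 | 1.05 × 23 / 35.95 = 0.67 | 4.8% |
| 1.05 | 17 | 1.05 × 20 / 35.95 = 0.58 | 3.4% |

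The classes made up of detected acids only are multiplied by T / (T − m): 37 / 36.58 = 1.011 to 37 / 35.95 = 1.029. On this reading MUFA and PUFA are overstated by about 1.1-2.9%.

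**Step 4, SFA if the short-chain mass is booked as other.** MUFA and PUFA are then not inflated, but SFA is low by the full m, 0.42-1.05 points.

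**Step 5, a low-dairy-fat comparison.** With no butter and 245 g skim milk at the section 5.1 limit of 0.5% fat, m is at most 245 × 0.005 × 0.10 × 9 / 2000 × 100 = 0.06% of energy. This is illustrative and is not a diet shown in the protocol.

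**The case against.** Several points on the other side have force.

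- **The calculation is not fully shown.** Section 6.1.8 sends the chromatograph output to SOP 5025 and takes its samples from SOP 5010; neither is reproduced. A reader might infer that MUFA and PUFA are certainly inflated. The document does not settle that, because the other column offers a second route and a later correction cannot be excluded. On either route in the text, however, C4-C8 does not reach SFA.
- **Attribution to diet rests on one menu.** A reader might infer a bias confined to a butter-based Diet A. The Diet B and C records are not shown, composites pool eight daily menus (sections 5.9 and 5.9.1), and the butter supplies about 15 g of 82 g fat in that menu. Larger error in diets with more dairy fat is likely; the pattern across the three diets is not documented.
- **Gravimetric fat includes lipid that is not fatty acid.** Scaling to it pushes every class upward, so the net absolute error in SFA is not fixed by this balance alone. The figures above are for the short-chain omission only, which that effect does not repair.
- **The consequence is limited.** A reader might infer that the lipid results, or a response per unit of SFA, are biased. The aims compare diets on blood measures, and no analysis per unit of measured SFA appears in the protocol. Fatty-acid classes serve documentation (section 5.9.2.2); the rapid quality check uses total weight, dry weight and total fat (section 5.9.2.1).
- **Safeguards exist.** A control composite is compared with independent data from the Nutrient Composition Laboratory, and composites are archived. The comparison would show the loss only if that laboratory measures C4-C8, which is not stated.

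**Conclusion.** The point holds as a mismatch between what is measured and what is reported: a C10-and-above quantity is scaled to all fat and called total SFA. For Diet A, Menu 1 at 2000 kcal the understatement is about 0.2-0.7 points of energy if section 6.0's scaling is applied to the detected peaks, or 0.4-1.05 points if the short-chain mass is booked as other. These sizes depend on the assumed C4-C8 share, butter fat content, true SFA and the 37% level for Diet A, and they describe one menu rather than a cycle composite.

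The effect is modest and confined to the documented fatty-acid composition and SFA contrast. It is worth correcting because that composition is the record of the exposure the trial varies.

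**What to change.** Assay the butter and whole-milk fat once for C4:0-C8:0. For each composite, multiply by the weighed butter and milk on its food record (section 5.9 requires one for every quality-control sample), scale the detected classes to total fat less this fraction, and add the fraction to SFA. By the balance above this returns S exactly when the fraction is right. Flag the added amount as source-derived.

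If that is not done, report the class as *SFA, C10 and above* and do not scale it to total fat.

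Do not fill the gap from the menu database alone. The assays exist to verify what was fed, and database values would make that part of the check circular.

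The cost is a few source assays and a change to the laboratory's calculation; sampling is unchanged. Section 5.1 has fat sources bought centrally, so one butter assay could serve all centers, but milk is bought locally and may need one assay per center. Section 5.11 already plans separate fatty-acid assays of the unit-food fat blends. The downside is that a small part of SFA is not measured directly in the composite.
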